Once all participant phlebotomy specimens have been obtained, we will be able to derive a predictive model for successful medical management vs. failure for all subjects. Separate predictive models will then be built for each treatment arm, and any differences found here will lay foundations for future research. Accurate assessment of gestational age (GA) can be a challenge in women who present with EPF, and GA may in fact be a confounder in the relationship between hormone levels and the nature of the demise. Depending on time of presentation relative to time of demise, biomarker levels may be more a reflection of the actual GA, or may in fact be impacted by duration of demise (i.e. β hCG, P_4 may start declining after demise occurs). We can utilize last menstrual period dating (LMP) with the caveat that LMP is not always certain. To overcome this measurement error problem, we will also analyze a

subset of women with a sure LMP and for whom ultrasound dating is consistent with LMP. If the model for this subset is consistent with the model for the full data, or GA is not found to significantly modify the relationship, only the full data model will be presented.

Biomarker levels will be summarized overall, and by treatment group, using standard descriptive statistics. We will use graphical methods, such as lowess smoothers, to determine the shape (linear or non-linear, potential cut-points for classifying levels) of the relationship between the biomarker level and probability of success, and subsequently for inclusion as predictors in a multivariable logistic model. We will analyze a subset of women with a sure LMP and for whom ultrasound dating is consistent with LMP separately for the most accurate analysis of the relationship between biomarker concentration and the characterization of an EPF that will respond well to medical management. We can compare this definitive LMP group to the group of women in whom LMP is unsure. We will calculate the sensitivity, specificity, and positive and negative predictive values for each biomarker. The predictive accuracy of different cutoffs will be evaluated using ROC curves.

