Logistic regression and classification and regression trees (CART) will be used to develop a predictive model for successful management of early pregnancy failure, which will serve as the basis for a clinical predictive index [66-68]. Our group has used this methodology with success [69,70]. Initially the predictive model will only include biomarkers, and then both biomarkers and epidemiologic and clinical characteristics will be considered in the predictive model. The sensitivity of the predictive index (i.e., proportion of patients with success who are defined as “high chance of success” by the rule) will be of primary interest [71]. The negative predictive value will also be calculated using the derived sensitivity and specificity with the population prevalence of success. This value is also of clinical interest.

For model building, we will enter all biomarkers that will have shown in the bivariate analysis at least borderline associations with the endpoints of interest ($p < 0.20$), as well as interaction terms that are suggested by the results of the explanatory model. Terms will then be removed from the model using a backward elimination procedure, removing factors which cause an insignificant change in the sensitivity of the model. To test the change in sensitivity between models (with and without the variables), we will use McNemar’s test. In particular, we will be comparing the proportion of correctly classified cases of success between models. The rule would involve calculating a score for each person, based on the actual values of the regression coefficients. The goal is to utilize all variables that improve the sensitivity of the model. Unlike the explanatory model, whose goal is to determine which variables are associated with success, the predictive models will be developed in order to determine which combination of variables best predicts the outcome. Additionally, variables and interactions included in the model must be biologically plausible.

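### Gestational age is named as a possible confounder of the biomarker associations, but the stated checks do not address confounding and adjustment for it is not guaranteed

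*Combined protocol and SAP*

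**What the plan says.** All of the following is in section 7.2, Statistical Methods, unless another section is named.

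- The problem is stated openly: "GA may in fact be a confounder in the relationship between hormone levels and the nature of the demise", and, depending on when a woman presents, "biomarker levels may be more a reflection of the actual GA". The first sentence speaks of the nature of the demise, but it stands in the paragraph that introduces the model for treatment success.
- The remedy, opening with "To overcome this measurement error problem, we will also analyze a", is a dating remedy: women whose menstrual dating is certain and agrees with ultrasound are analysed as a subset.
- The reporting rule has two alternative conditions. The first is agreement of the two models: "If the model for this subset is consistent with the model for the full data". The second needs no such agreement and is enough by itself: "or GA is not found to significantly modify the relationship, only the full data model will be presented". No criterion for consistency, test or significance level is given.
- For single markers: "We will calculate the sensitivity, specificity, and positive and negative predictive values for each biomarker". No GA term is mentioned. Markers also go into a multivariable logistic model whose covariates are not listed.
- For the predictive model, the starting point is narrow: "Initially the predictive model will only include biomarkers". A later step widens it: "then both biomarkers and epidemiologic and clinical characteristics will be considered in the predictive model". Markers enter on an unadjusted p < 0.20. Terms are removed when their removal does not significantly change sensitivity (McNemar's test).
- Earlier in 7.2, the regression of success on treatment keeps covariates that shift the unadjusted ratio by at least 10%. GA is not named there, and the rule is not tied to the biomarker models.

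**The concern.** Confounding and effect modification are different things. A confounder distorts the marker's coefficient when it is left out, and it is dealt with by putting it in the model as a main effect. A modifier changes the marker's coefficient across its own levels, and it is found through a product term. A variable can be a strong confounder with no product term at all. The plan names the first problem and tests for the second.

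The other step does not help either. Better dating sharpens GA, but a marker that tracks GA tracks it in the well-dated women too. Agreement between subset and full data therefore says nothing about confounding.

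At stake is how the secondary objective in section 2 is read. Hypothesis (1) concerns markers of decidualisation and trophoblast function. Hypothesis (2) combines markers with clinical characteristics. Both are worth much less if a marker carries only what GA already tells the clinician. The documents make this plausible: eligibility spans 5 to 12 completed weeks (section 4.1), and section 7.4 allows that failure may differ by week of gestation. Randomisation gives no protection, because markers are not randomised.

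**Working it through.** **Where GA could be adjusted for**

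| Analysis in 7.2 | GA term stated? |
|---|---|
| Single-marker accuracy and ROC curves | No |
| Multivariable logistic model of markers | Covariates not listed |
| First predictive model | No, biomarkers only |
| Second predictive model | Possible as a clinical characteristic; not named; removable on change in sensitivity |
| 10% change-in-estimate rule | Stated for success by treatment; not linked to markers |

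So adjustment is possible but not secured.

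**What the 'or' does.** Let A be agreement of the subset with the full data, and B a non-significant modification test. The rule presents only the full-data model if A or B holds. If A fails and B holds, the subset model disagrees and still goes unreported. The subset is to be analysed in any case; what depends on the rule is whether it is shown.

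**Size.** The plan gives no figure on this point. Taken from section 7.1: 300 women, and success of 85% and 70%, which average (85 + 70)/2 = 77.5% at 1:1. As background, the plan's 134 per group for those rates is reproduced exactly with a two-sided alpha of 0.05, 80% power (inferred) and a continuity correction; without the correction it is 121. Nothing below rests on it.

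Assumed, because the documents do not give them: the failure odds ratio (OR) per SD of GA, and the marker-GA correlation ρ.

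Model for a pure proxy, with g and e independent standard normal:
- marker: m = ρ·g + √(1 − ρ²)·e
- success: logit P = a − ln(OR)·g, with a set so that mean success is 77.5%

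Given g, the true coefficients of m and of m×g are both zero. Three logistic models were fitted to each of 2,000 simulated trials per setting: m alone; m + g; m + g + m×g. The simulation error of any percentage is at most √(0.5 × 0.5/2000) = 1.1 points.

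| OR | ρ | Interaction p ≥ 0.05 | Marker p < 0.05, unadjusted | Marker p < 0.05, adjusted | Interaction p ≥ 0.05 and unadjusted marker p < 0.05 |
|---|---|---|---|---|---|
| 1.3 | 0.3 | 95.0% | 8.2% | 4.2% | 7.6% |
| 1.3 | 0.5 | 95.8% | 14.0% | 4.6% | 13.6% |
| 1.3 | 0.7 | 95.4% | 24.8% | 4.9% | 23.6% |
| 1.5 | 0.3 | 95.7% | 14.4% | 5.0% | 14.1% |
| 1.5 | 0.5 | 95.8% | 28.8% | 4.6% | 27.3% |
| 1.5 | 0.7 | 94.4% | 53.7% | 4.6% | 50.8% |
| 2.0 | 0.3 | 95.5% | 27.6% | 4.3% | 26.5% |
| 2.0 | 0.5 | 95.0% | 66.4% | 4.9% | 63.4% |
| 2.0 | 0.7 | 96.0% | 91.1% | 4.7% | 87.5% |

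At the plan's entry threshold of p < 0.20, the proxy passes in 25% to 98% of trials unadjusted and in 19% to 21% adjusted. The median unadjusted marker OR for success runs from 0.93 to 0.63.

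The interaction column stays near 95% however strong the confounding. That is simply one minus the significance level, since no interaction was simulated. It shows that the test does not respond to confounding; it does not forecast what this trial will report.

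**The case against.** Several points on the other side are sound.

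- A reader might infer that the reporting rule sends confounded markers through unadjusted, or that some 95% of trials would present only a confounded model. The documents do not support that. The rule chooses between the full sample and the well-dated subset, not between adjusted and unadjusted models. Nothing says that the full-data model omits GA.
- The plan goes on from biomarkers alone to biomarkers with clinical characteristics. GA is an obvious candidate there, being an eligibility criterion and a suggested source of differing failure rates. If the 10% rule were applied to a marker, it would flag GA in 34% of simulated trials at OR 1.3 and ρ 0.3, in 91% at 1.5 and 0.5, and in nearly all at 2.0 and 0.7. What remains is that the plan does not apply it there, and that backward elimination looks at sensitivity, not at the marker's coefficient. GA could be dropped while its proxy stays.
- The aim is largely prediction, and a proxy for GA does predict. A reader might infer that a significant proxy would make hypothesis (1) false. It would not: the unadjusted association is genuine. The damage is to a biological reading and to any claim of value beyond GA.
- The word 'modify' may be meant loosely, as 'alter'. The text does not say so.
- GA is hard to measure in these women, as the plan itself notes, so adjustment will leave some confounding. Levels may also reflect time since demise, which could weaken the correlation with GA. Both are reasons to report with and without GA, not to leave GA unspecified.

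**Conclusion.** The point holds in a limited form. The plan raises confounding by GA and then specifies checks that cannot reveal it. One of those checks, on its own, can keep a disagreeing subset model out of the report. Adjustment for GA is neither specified nor guaranteed.

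For a marker that is purely a proxy, the simulated chance of significance at 0.05 is 8% to 91% unadjusted and 4% to 5% adjusted; at the middle setting (OR 1.5, ρ 0.5) it is 29% against 5%. These figures rest wholly on the assumed ORs and correlations, on normally distributed GA measured without error, and on a marker with no effect of its own. They show the direction and possible scale, not an expected error rate for this trial.

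The matter concerns the secondary, biomarker objective. The primary comparison of treatment arms is unaffected. The change is worth making because it is almost free.

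**What to change.** In section 7.2:

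1. Keep the planned biomarkers-only model.
2. Add GA as a prespecified main effect, not subject to elimination, in the biomarker association models and in the biomarker-plus-clinical model.
3. Define GA by one dating rule available for all women, for example ultrasound-based, and say how it applies to anembryonic gestations. Use menstrual dating as a sensitivity analysis in the well-dated subset.
4. Report each marker's OR and AUC with and without GA.
5. Report full-data and subset results whatever the interaction test shows, and present that test as a secondary result that decides nothing.
6. State that dating error leaves some residual confounding.

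The cost is SAP wording and one extra column in the biomarker table. No new data are needed, because GA is already required for eligibility. At 77.5% success, 300 women give about 300 × 0.225 = 67.5 failures, so one further prespecified term is affordable in the models for all women; the arm-specific models will be tighter.

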Complete expulsion rates for women using misoprostol for miscarriage completion vary significantly in the published literature, from 25-86% [5,6,8,25-30]. This variability is due, in part, to the fact that studies have used differing definitions of pregnancy failure; as well as varying drug doses, delivery modes, criteria for success, and outcome measures [5,6,8,26,31-40]. The earlier studies helped to reveal the relative merits of different drugs, doses and routes. The data support that misoprostol 800 µg vaginally provides the best toxicity/efficacy profile [6,8]. The definitive, multi-center, randomized trial comparing surgical management to medical management with vaginal misoprostol (the 2005 MEPF trial [9]) in women through approximately 12 weeks gestation (in which our team at both centers collaborated), reported successful uterine evacuation in 71% of participants with one dose of misoprostol (800 µg vaginally). These complete abortion rates contrast dramatically with the published 98% success rate for uterine curettage [9]. While the MEPF trial found misoprostol to be "non-inferior" to surgery due to trial design, few could argue that 60-71% success compares fairly with the 98% that surgery boasts. Nevertheless, misoprostol is now widely used in the U.S. and across the globe for management of EPF; the regimen tested by Zhang et al. [9] has become the evidence-based standard of care. The efficacy of misoprostol for medical management of pregnancy failure in the first trimester was illustrated in a large, well-designed trial in which 652 women with missed, incomplete, or inevitable abortion were randomly assigned 3:1 to receive 800 µg misoprostol intravaginally or undergo vacuum aspiration as cited above [9]. The rates of complications such as fever, infection, and excessive bleeding, and emergency room visits, were very low and similar to those from uterine aspiration.

Published clinical predictors of treatment success with misoprostol for EPF include lower abdominal pain, vaginal bleeding within 24 hours of presentation, and nulliparity [25]. Misoprostol alone is highly

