The highly effective, safe combination regimen described above may also effectively treat women with EPF [11,12,39,58]. Our preliminary observations [11] strongly support this. However, this regimen needs to be rigorously tested in a sufficiently powered clinical trial [5]. The biologic basis for why a combination regimen should be more effective and safe than misoprostol alone, even in the cases of a failed pregnancy, has been preliminarily described. We and others have hypothesized that those failed pregnancies that do not respond to uterine evacuation with misoprostol alone appear to represent a subset of EPF in which the invasion of the extravillous trophoblast into the decidualized endometrium is altered [24,59]. This enhanced "attachment" of the pregnancy may be due to a direct trophoblastic effect, and/or may be due to characteristics of the decidualized endometrium. There is evidence for a direct supportive effect of P_4 on human trophoblast function [60], and therefore, this effect could be inhibited by the use of mifepristone. In addition, mifepristone also has anti-glucocorticoid activity, with relatively high binding affinity for the glucocorticoid receptor [20,21]. Since glucocorticoids are critical to

the function of human trophoblast cells [61], the presence of mifepristone could lead to decreased proliferation, differentiation, and/or invasive properties of the trophoblast – even in a failed pregnancy [62].

2 Study Objectives

Primary Objective

To compare the effectiveness of combination treatment (mifepristone premedication plus single-dose misoprostol) to single-dose misoprostol (standard of care) for the management of early pregnancy failure.

Our hypothesis states that the combination of mifepristone and single-dose misoprostol will be more effective than single-dose misoprostol alone, and will reduce the proportion of failed medical treatments (those who require repeat dosing or surgery) by at least 20% in 300 women seeking treatment for first trimester embryonic/fetal demise and anembryonic gestation.

Secondary Objective

[figure not shown]
To test the ability of trophoblastic and endometrial biomarkers to predict which women are most likely to succeed with medical management of early pregnancy failure and to derive and internally validate a prediction model designed to guide individualized counseling and treatment for early pregnancy failure.

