proportion of successful outcomes within the two treatment groups will initially be compared via calculation of relative risk and odds ratio. The relative strength of the difference in success between groups, as measured by the odds ratio, will be further evaluated via logistic regression. The study population will be summarized overall, and by treatment group, using standard descriptive statistics. Bivariate methods, such as chi-square or Fisher's exact tests (categorical variables) and t-tests or Mann-Whitney U tests (continuous/ordinal variables) will be used to compare the treatment groups' demographic and clinical characteristics. These same methods will be used to initially evaluate differences in the success by demographic and clinical characteristics. The bivariate analyses will be used to select variables for inclusion in subsequent multivariable regression models. We will stratify our results by presenting symptomatology (spotting/cramping etc.). Multivariable logistic regression will be used to evaluate the odds of success within each treatment arm and adjusted for demographics (including race and ethnic variation) and clinical variables that may affect the odds of success. The variables found to be related to the success rate on the bivariate level will be entered one at a time into the model, iteratively comparing the adjusted odds ratios. The final regression models will include the treatment group, study sites, characteristics associated with success rate at the $p < 0.1$ level, as well as covariates that altered the unadjusted ratios by at least 10%. Graphical techniques, such as lowess plots, will be used to assess the assumptions of the models.

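### The prediction plan has no clinical-only benchmark and no block test of the biomarkers over clinical data, so it cannot reliably show what the blood markers add

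*Combined protocol and SAP*

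**What the plan says.** The secondary objective (section 2) is "To test the ability of trophoblastic and endometrial biomarkers to predict which women are most likely to succeed with medical management", and to derive and internally validate a model for individualized counseling and treatment. Its first hypothesis is that pre-treatment markers predict success. Its second is that markers combined with clinical characteristics predict accurately. Neither states a gain over clinical data.

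Section 7.2 gives the model order: "Initially the predictive model will only include biomarkers, and then both biomarkers and epidemiologic and clinical characteristics will be considered in the predictive model". Biomarkers enter if their bivariate p-value is below 0.20. Backward elimination follows, "removing factors which cause an insignificant change in the sensitivity of the model". The test is specified as "To test the change in sensitivity between models (with and without the variables), we will use" McNemar's test. ROC curves compare simplified with fuller rules, and CART with logistic regression.

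Three other places bear on the point:

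- Section 1.2: "Published clinical predictors of treatment success with misoprostol for EPF include lower abdominal pain, vaginal bleeding within 24 hours of presentation, and nulliparity".
- Section 7.2, primary analysis: "Multivariable logistic regression will be used to evaluate the odds of success within each treatment arm and adjusted for demographics" and clinical variables. Biomarkers are not listed there. The prediction text sets its own models apart from this one: "Unlike the explanatory model, whose goal is to determine which variables are associated with success".
- Section 7.2, on gestational age: "GA may in fact be a confounder in the relationship between hormone levels and the nature of the demise".

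**The concern.** Bleeding, pain, parity and gestational age are known from history and ultrasound before any assay is run. A blood marker is useful for counseling only if it improves on them. The protocol itself gives reason to doubt this: it cites three clinical predictors and says that marker levels may reflect gestational age.

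The two planned models share the biomarkers and differ only in the clinical terms. Comparing them therefore measures the contribution of the clinical terms. The comparison that would isolate the markers needs a clinical-only model as its base, and none is named.

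Two errors could follow. A marker that merely tracks gestational age could be reported as a predictor from the biomarker-only model and the single-marker ROC results. A marker that truly adds information could be missed, because the only conditional check is weak.

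**Working it through.** **1. The plan's own figures.** The prediction aim has no stated target: no AUC, sensitivity or increment. The only sizing figure is 134 per group for 85% versus 70% success (section 7.1). Assuming two-sided alpha 0.05 and 80% power:

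- Without continuity correction: n = [1.96·√(2·0.775·0.225) + 0.8416·√(0.85·0.15 + 0.70·0.30)]² / 0.15² = (1.1575 + 0.4889)² / 0.0225 ≈ 120.5, rounded up to 121.
- With continuity correction: n' = (120.5/4)·[1 + √(1 + 4/(120.5·0.15))]² ≈ 133.5, rounded up to 134. This reproduces the plan.

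At 150 per group, expected failures are 150·0.30 = 45 and 150·0.15 = 22.5, in total 67.5. Successes are 232.5/300 = 77.5%.

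**2. What each comparison measures.** I took one clinical variable x and one marker m, both standardized, with a logistic outcome at 77.5% success. The coefficients and correlations are assumptions; the documents give none. Large-sample AUCs (200,000 subjects):

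| Assumed truth (log-odds of x, m; correlation) | m only | x only | both | Planned step (both − m) | Added value of marker (both − x) |
|---|---|---|---|---|---|
| Marker is a proxy (0.8, 0; 0.7) | 0.645 | 0.705 | 0.705 | 0.060 | 0.000 |
| Marker adds (0.5, 0.5; 0.2) | 0.657 | 0.655 | 0.702 | 0.045 | 0.046 |
| Only marker matters (0, 0.7; 0.2) | 0.685 | 0.536 | 0.685 | 0.000 | 0.149 |

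Planned steps of similar size (0.060 and 0.045) arise with an added value of zero and of 0.046. The largest added value goes with a planned step of zero. So the planned step carries no usable information on what the markers add. In the proxy row the marker alone (0.645) would also clear the AUC > 0.6 entry condition for CART.

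**3. A marker with no effect beyond gestational age.** Assumed: n = 300, gestational-age odds ratio 0.6 per SD, correlation 0.6.

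- The marker's log odds ratio on its own is about 0.6·ln 0.6 = 0.6·(−0.511) = −0.307, an odds ratio of about 0.74.
- It is significant on its own at 5% in about 55% of simulated trials. Over correlations 0.4 to 0.7 and odds ratios 0.6 to 0.7 the range is about 19% to 66%.
- It passes the plan's p<0.20 screen in about 80%. A pure-noise marker passes in 20%.
- Given gestational age, the likelihood-ratio test rejects in 6%, close to nominal.

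**4. A marker with real added value.** Assumed: n = 300, odds ratio 0.6 per SD for the marker and for the clinical variable, correlation 0.2.

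- McNemar's test on sensitivity, with versus without the marker, detects it in about 16-28% of trials, depending on the cutoff (16% at 0.5).
- The likelihood-ratio test detects it in 93%.

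With success near 77%, sensitivity at a cutoff of 0.5 is already about 98%, so few women can change classification and McNemar's test has few discordant pairs to work with.

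**The case against.** Four points can be made for the plan.

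- *A clinical regression without biomarkers is planned.* True, so a reader who infers that there is no clinical-only model of any kind goes too far. But that regression is explanatory, and no discrimination measure or validation is planned for it. It is not a prediction benchmark.
- *The combined model does test markers given clinical terms.* Also true. One might infer that the trial cannot say anything about added value; that is too strong, since the with/without step gives a partial answer and a clinical-only model could be fitted later. But the step works term by term, on sensitivity alone, at an unstated cutoff, never on the markers together, and step 4 above shows how often it misses.
- *The two models match the two hypotheses.* They do. The plan omits a comparison; it does not contradict its objective.
- *Gestational age is handled.* The sure-LMP subset addresses dating error, and the modification check addresses interaction. Neither measures gain over gestational age.

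A further tempting inference is that uninformative markers will stay in the final index. The documents do not support it. In simulations of the elimination step with a proxy marker, McNemar's test kept it in 0% to 27% of trials in the gestational-age setting, depending on the assumed cutoff. It may well be dropped from the combined model. What remains is that it would look predictive in the biomarker-only results.

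**Conclusion.** The point holds as an omission in the secondary prediction aim. The named sequence answers what clinical data add to markers. The reverse comparison is left to a check that found a real gain in about 16-28% of simulated trials, where a likelihood-ratio test found it in 93%. The plan as written therefore cannot reliably show what the markers add.

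The sizes rest on assumed odds ratios, correlations and cutoffs, with one clinical variable, one marker and no prior selection. With several screened markers, the power of any test would be lower. The structural finding in step 2, that the planned step and the added value are different quantities, does not depend on those values. The primary treatment comparison is unaffected. This should be changed, but it does not threaten the trial's main result.

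**What to change.** In the model-building text of section 7.2:

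1. Prespecify a small clinical reference prediction model, fitted first in the pooled data, from baseline variables: presenting bleeding and pain symptoms, parity, gestational age, site and treatment arm.
2. Add the biomarkers as a block.
3. Report the likelihood-ratio test and the bootstrap-corrected change in AUC, with confidence interval, as the measure of added value. The bootstrap is already planned for internal validation.
4. Keep the biomarker-only model as descriptive.

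The cost is SAP wording and one extra model, with no new patients or visits. Two cautions apply. The section 6.2 list of baseline items does not name bleeding or pain explicitly, although section 7.2 plans to stratify by presenting symptoms; the case report form should be checked to confirm that they are recorded before treatment. And with about 67 expected failures, 22-23 of them in the combined arm, the clinical set must stay small and the arm-specific models should be labelled exploratory.
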